We performed a long-term study to assess the safety and potential of BCI-FES therapy. Nine chronic stroke subjects (>6 months post-ictus) with gait impairment due to foot-drop underwent 12 sessions of BCI-FES therapy (3 sessions/week, for 4 weeks). The primary outcome measure was gait velocity. Secondary outcomes were dorsiflexion active range of motion (AROM), leg motor Fugl-Meyer score, gait endurance (6-min walk test), and fall frequency. These outcomes were assessed before, on a weekly basis, and 1 month after completion of the BCI-FES therapy (Fig. 3). No subjects experienced a significant decrement in any outcome measure and there were no adverse events, indicating that BCI-FES therapy is safe. In post-hoc analysis, 6 out of 9 (66.7%) subjects had a significant improvement in gait velocity at 1 month post-therapy (average increase of 51%, or  $0.21 \pm 0.15$  m/s). While no spatial cortical reorganization was observed in any subject at the end of therapy, the Cz channel (electrode over the foot motor area) exhibited an increase in alpha- and beta-band event-related desynchronization/synchronization (ERD/ERS) magnitude in 5 of these 6 (83.3%) subjects. Conversely, these EEG changes did not occur in the 3 subjects with no gait velocity improvement. This suggests the existence of a neural process underlying gait velocity improvements. Subjects with low gait velocity (<0.4 m/s) and poor dorsiflexion AROM (<5 degrees) at baseline were 150% more likely than those with moderate-to-high gait velocity (>0.4 m/s) or good-to-excellent AROM (>5 degree) to experience an increase in gait velocity. This highlights a potential promise of BCI-FES therapy in that it may be accessible and beneficial to stroke survivors whose baseline motor functions are too low for current or emerging interventions.

Describe the primary outcome variable(s), secondary outcome variables, and predictors and/or comparison groups as appropriate for the stated study objectives/specific aims:

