Aim 1: The primary outcome measure will be gait velocity, which is directly linked to disability and social re-integration after stroke. Gait velocity will be assessed by measuring the time to traverse the middle 6 m of a 10-m walkway (5 repetitions/assessment). Secondary outcomes include: 1. Gait endurance: The distance walked over 6 minutes. 2. Fall Frequency: Number of falls experienced weekly. 3. Leg Motor Fugl-Meyer (FM) Score: Assessed according to the FM rating system. 4. Dorsiflexion Active Range of Motion (AROM) and torque: The paretic foot will be placed in an articulated brace which maintains the ankle at neutral during idling, while fixing the tibia perpendicular to the ground and the femur horizontal to the ground. The brace will be instrumented with an electro-goniometer and torque meter to automatically measure the maximum dorsiflexion AROM and torque (over 3 trials). 5. EEG Map: Subjects will undergo 64-channel EEG recording as they engage in 100 alternating 10-s long epochs of idling and attempted dorsiflexion. The EEG ERD/ERS, defined as the drop/rise in alpha (8-12 Hz) and beta (13-30 Hz) band power during attempted dorsiflexion (compared to idling), will be calculated and averaged over all epochs and across all channels. A pre-intervention baseline for each outcome will first be established. Subsequently, measurements will be performed at 1 week intervals during the intervention phase (total of 3), immediately after the intervention phase, as well as 1 and 3 months after completion of interventions. The primary efficacy outcome and endpoint will be gait velocity immediately after the intervention phase. Aim 2 (subgroup analysis of Phase II clinical trial) Since stroke is a heterogeneous disease, responsiveness to rehabilitation therapy is not uniform across all subpopulations. Hence, it is important to ensure that any new therapy, e.g. BCI-FES therapy, is matched to subpopulations that will benefit the most. The following set of baseline characteristics will be assessed during the pre-intervention phase (Fig. 6, Phase 2) for Groups 1 and 2 to determine which features influence responsiveness to BCI-FES therapy: 1. Baseline gait velocity, dorsiflexion AROM and torque: Baseline gait velocity and dorsiflexion AROM and torque will be taken from Aim 1. 2. TA volitional electromyogram (EMG): TA EMG will be assessed by having subjects attempt dorsiflexion while seated with tibia perpendicular to ground. EMG will be acquired by a bioamplifier with surface electrodes placed over the TA muscle. Subjects will be categorized as either

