#### **Statistical Considerations**

Is a statistical analysis plan appropriate for this qualitative study design?

Yes

Describe the statistical methods for the stated specific aims and hypotheses. Your analysis plans should match the stated study specific aims and hypotheses:

Aim 1: The study design is a parallel randomized controlled trial with two arms: BCI-FES dorsiflexion therapy and dose-matched conventional physical therapy. A total of 80 subjects (which includes 10% attrition) will be randomized with 1:1 ratio into the two study arms. The primary outcome is gait velocity and the secondary outcomes are gait endurance, fall frequency, leg motor FM score, and dorsiflexion AROM and torque. Outcomes measures will be evaluated at baseline, weekly during therapy, immediately post-intervention, and 1- month and 3-months post-therapy. The primary efficacy analysis (with intent-to-treat analysis with respect to treatment randomized) will be based on a linear mixed model (LMM) with gait velocity measured at baseline weeks 1-4 (time 0, 1, 2, 3, and 4) with time, treatment group and group by time interaction assess the difference in the rates of change (improvement) in gait velocity between treatment groups. Model estimation will be based on restricted maximum likelihood (REML) with unstructured covariance among repeated measurements over time. The LMM will also be applied to evaluate group difference for secondary outcomes and secondary endpoints at 1- and 3-months post-therapy. In order to determine if  $\mu$  and  $\beta$  ERD/ERS significantly changes over the 4 weeks of therapy, the ERD and ERS magnitude will be calculated for each EEG channel across all attempted dorsiflexion epochs, and for each assessment. The Mann-Whitney U test will be used to determine if any significant changes in the magnitude of ERD/ERS at each assessment with respect to the baseline. Based on the findings, each subject will be categorized as demonstrating significant changes in ERD/ERS or not. Next, all subjects will also be categorized on whether they experienced a detectable increase in gait velocity (defined as an increase in gait velocity of  $>0.16$  m/s with respect to baseline). A Chi-square test will be used to assess if there is a difference between the proportion of those with changes in ERD/ERS magnitude in those who had gait improvement within the BCI- FES therapy group. This will also be repeated for the control group. In addition, to determine if the presence of significant ERD/ERS changes was affected by group, the Chi-square test will be repeated by using BCI-FES group as the observation and the control group as the expected values. Aim 2: Data from Aim 1 will be used for analysis in this aim. The primary outcome is gait velocity immediately post-BCI-FES therapy, and the secondary outcomes are the same as in Aim 1. To test whether specific stroke features (e.g. baseline gait velocity, dorsiflexion AROM, etc.) modify response to treatment over

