**Power Analysis:** For Aims 1 and 2, the power analysis was based on a LMM with two treatment groups and 5 repeated measures (baseline and after weeks 1-4) with a significance level of 0.05. Previous studies have examined the clinically meaningful gait improvement (minimal clinically important difference) of 0.16 m/s, including a multicenter randomized clinical trial that includes conventional physical therapy. Thus, to ensure clinically meaningful effect size, we assume conventional therapy will have an improvement of 0.25 m/s after 4 weeks of treatment. Data from prior studies as well as our own preliminary data (n=9) found that the between-subject variance in gait velocity of about 0.16 m/s and the within-subject correlation of about 0.95. Table 1 below shows the power to detect improvement of BCI-FES over conventional therapy of 30% - 40%. Thus, for the proposed study with n=80 patients (40 per arm) has 92% to 94% power to detect an effect size/improvement of 35% for various between-subject variance (0.15 m/s to 0.17 m/s) in determining treatment efficacy (Aim 1). We note that n=80 total has been intentionally inflated in order to accommodate the objectives of aim 2 to examine modifying factors, such as TA MEP (primary modifying factor), on treatment. That is, for n=30 per arm the power to determine efficacy (aim 1) is 85% for detecting an effect size/improvement of 35% (between-subject variance 0.16 m/s); thus, increasing to n=40 allows for detecting modifying factor on treatment (aim 2) when the interaction effect smaller (effect size 28% can be detected with 79% power). Table 1: Power to detect improvement in gait velocity due to BCI-FES over conventional therapy for n=80 with various between-subject variance (aim 1). Between-Subject Variance Effect Size (Improvement) 0.15 0.16 0.17 30% 87.3% 85.2 % 83.0% 35% 94.5% 93.5% 92.1% 40% 98.3% 97.7% 97.0% Aim 3: Total sample size of n=20 will have 82% power to detect an R-square of 0.16 (attributed to the effect of interest, e.g., w x group) adjusted for baseline measurement and main effects whose total contribution R-square is 0.5 (for 3 independent variables) in a multiple regression model.

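### The yes/no label for a significant ERD/ERS change has no stated rule or error control, and the two definitions of the EEG measure conflict

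*Combined protocol and SAP*

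**What the plan says.** The Aim 1 text in Statistical Considerations states that "the ERD and ERS magnitude will be calculated for each EEG channel across all attempted dorsiflexion epochs, and for each assessment". A Mann-Whitney U test is then used to "determine if any significant changes in the magnitude of ERD/ERS at each assessment with respect to the baseline". From the results each subject is put into one of two classes, changed or not changed. That class feeds three chi-square comparisons: against gait improvement within the BCI-FES arm, the same within the control arm, and between arms.

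The EEG Map outcome in Study Design (repeated in Background & Purpose of the Research) is defined differently. There ERD/ERS "will be calculated and averaged over all epochs and across all channels".

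Neither section says which significance level applies to these tests, how many positive tests make a subject changed, which channel, band, visit or direction counts, or how multiplicity is handled. The pilot result behind the analysis was narrower: "the Cz channel (electrode over the foot motor area) exhibited an increase in alpha- and beta-band" ERD/ERS magnitude in 5 of the 6 subjects whose gait improved, and in none of the 3 whose gait did not.

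**The concern.** The label comes from many tests within one person, and the plan does not limit how many can trigger it. The more tests that can trigger it, the more subjects without any true change are called changed. A label that many unchanged subjects carry has little variation left to relate to gait improvement or to arm. The label also depends on which of the two definitions is followed and on a rule not yet written. If that choice is made after the EEG results are seen, it adds analytic flexibility.

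A second problem sits beneath the first. The test seems intended to rank epochs from one session against epochs from another. It then asks whether two sessions differ, which is a weaker question than whether therapy changed the subject.

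**Working it through.** The plan gives no test count, false-positive rate or power for this label, so there is no figure to reproduce.

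**Inputs**

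- Channels and epochs (Study Design): "Subjects will undergo 64-channel EEG recording as they engage in 100 alternating 10-s long epochs of idling and attempted dorsiflexion". If the 100 counts both kinds, there are 50 dorsiflexion epochs per assessment.
- Bands (Study Design): "drop/rise in alpha (8-12 Hz) and beta (13-30 Hz) band power", so 2.
- Assessments (Study Design): "measurements will be performed at 1 week intervals during the intervention phase (total of 3), immediately after the intervention phase", so 3 + 1 = 4 in the therapy period, or 6 with the 1- and 3-month visits.
- Level: the phrase "with a significance level of 0.05" belongs to the power analysis for Aims 1 and 2 only. Two-sided 0.05 is assumed here.
- Rule: any p < 0.05 labels the subject. This is an assumption, because the plan states no rule.

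**Chance that an unchanged subject is labelled changed**

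For m independent tests this is 1 − 0.95^m. The simulation used Mann-Whitney tests of 50 v 50 epochs, a baseline shared across visits, equally correlated channels and no true change. Band correlation was 0.3 in the 64-channel runs and 0 to 0.6 in the channel-averaged runs.

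| Reading | Tests m | Independent | Simulated |
|---|---|---|---|
| Channel average, 4 visits | 2 × 4 = 8 | 34% | 26–30% |
| Channel average, 6 visits | 2 × 6 = 12 | 46% | 34–37% |
| 64 channels, post visit only | 64 × 2 = 128 | 99.9% | 91%, 72%, 40% at channel correlation 0.5, 0.7, 0.9 |
| 64 channels, 4 visits | 64 × 2 × 4 = 512 | about 100% | 100%, 98%, 95%, 77%, 63% at 0.5, 0.7, 0.8, 0.9, 0.95 |

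A further set of runs agreed within a few points: 99% and 82% over 512 tests at correlation 0.7 and 0.9, and 92% and 43% for the post visit only at 0.5 and 0.9.

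**Session-to-session shift**

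Suppose epochs are the replicates and a session's ERD/ERS level varies by s epoch-SDs for reasons other than therapy. The difference between two sessions then has SD √(2/50 + 2s²), while the test allows only for √(2/50) = 0.20.

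- s = 0.1: √0.06 = 0.245, so a nominal 5% test rejects about 11% of the time.
- s = 0.2: √0.12 = 0.346, about 26%.
- s = 0.4: √0.36 = 0.60, about 51%.

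At s = 0.2, simulated Bonferroni correction still labelled 51% of unchanged subjects over 8 tests. Over 512 tests at 0.05/512 = 0.0000977 each, with channel correlation 0.7, it labelled 48%. With no shift, the same correction held the rate below 5%.

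**Cost to the chi-square comparisons (illustrative)**

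With false-label rate f, a true proportion p becomes p + (1 − p)f. Take 18 gait improvers and 18 non-improvers in one arm, with true change in 83.3% (the pilot's 5 of 6) and an assumed 20%.

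- f = 0: 0.833 v 0.20, power 99%.
- f = 0.34: 0.890 v 0.472, power 79%.
- f = 0.90: 0.983 v 0.920, power 14%.
- f = 0.95: 0.992 v 0.960, power 9%.

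Between arms, the Progress Report's 62 randomized in Aim 1 give about 31 per arm. With assumed true change in 60% v 30%, an ordinary two-proportion comparison has 67% power at f = 0. At f = 0.34 the proportions are 0.736 v 0.538 and power is about 37%. These are normal approximations and rough at extreme proportions.

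**The case against.** A reader might infer that nearly every subject will be labelled changed and that the trial therefore cannot answer its EEG question. The documents do not support that. They state no rule under which any channel, band or visit suffices; they state no rule at all. The all-channel average in Study Design cuts the tests from 512 to 8, and the false-label rate is then roughly one in three or lower. Even over 512 tests the rate depends on inter-channel correlation, which the documents do not give.

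The session-shift argument also has limits. ERD/ERS is measured relative to idling in the same recording. If it is expressed as a ratio, a simple gain or impedance change would largely cancel, though differences in alertness or cap placement might not. The plan does not say outright that epochs are the replicates. Read literally, the Study Design average over all epochs leaves one value per band and assessment, with nothing for a within-subject test to rank.

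False labels that fall equally on both arms, and on improvers and non-improvers, do not by themselves create an association. They cost power. The primary gait-velocity model and the sample size do not use the label, Aim 2 uses baseline ERD/ERS, and Aim 3 uses EEG–EMG coherence.

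All of this limits the size of the problem but does not remove it. The most favourable reading that still uses all four therapy-period visits gives a false-label rate over five times 5%, and the two definitions cannot both be followed.

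**Conclusion.** The labelling rule is undefined and has no error control, and the two sections describe different EEG measures. If any p < 0.05 counts, unchanged subjects are labelled changed in about 26–34% of cases on the channel-averaged reading. On the per-channel reading it is about 63–100% over the therapy period (assumed channel correlation 0.95 to 0.5) and about 40–92% for the final visit alone (0.9 to 0.5). If epochs are the replicates, any session shift raises these rates, and multiplicity correction does not remove that part; the size of the shift is an assumption. The consequence is lost power and an ambiguous result for the EEG question, with no effect on the primary gait-velocity analysis. This should be fixed, but it does not threaten the trial's main conclusion.

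**What to change.** Before the EEG analysis:

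1. Reconcile Study Design (and its repeat in Background & Purpose of the Research) with Statistical Considerations on one EEG measure. The candidates already in the documents are Cz, as in the pilot, and the all-channel average. Cz rests on a post-hoc result in nine subjects, and Study Design notes that the spatial distribution may alter after stroke, so the choice needs a stated reason.
2. Replace the epoch-level Mann-Whitney label with one continuous value per subject and band: change in ERD/ERS magnitude on that measure from baseline to immediately post-intervention. Use it, with the subject as the unit, for the arm comparison and for the relation to gait change, with Holm correction over the two bands.
3. Report other channels and visits descriptively.
4. If a yes/no label is kept, base it on that single measure, that visit and a stated direction.

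This needs revised wording and no new data. The costs are that changes confined to other channels or visits become exploratory, and that an outcome is being redefined late. The Progress Report says enrolment and treatment are complete, with final assessments and analysis remaining. The choice must therefore be documented as made before any unblinded EEG analysis.

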**Progress Report**

## **UCI Progress**

**Please provide a detailed description of the progress of the study, including a brief summary of any interim findings or trends, and plans for the next approval period:**

Our phase 2 clinical trial has concluded recruitment, enrollment and treatment. The plan for the next approval period is to complete post treatment assessments and data analysis. Interim data was reviewed confidentially by the DSMB at their meeting in November 2023 and approved. The DSMB Meeting report was uploaded to the attachment section. Subject status breakdown: Aim 1: 168 assessed for eligibility; 106 were ineligible, 62 were randomized to study; 54 received intervention per protocol and completed all assessments, 1 withdrew from treatment but completed assessments, 4 withdrew consent from study, 2 were removed by physician; 1 is ongoing for final assessment; Aim 3: 23 assessed for eligibility; 13 were ineligible, 10 were randomized to study; 8 received intervention per protocol and completed all assessments, 0 withdrew from treatment but completed assessments, 0 withdrew consent from study, 0 were removed by physician; 2 are ongoing for final assessment. Aims 1 and 3 were the only 2 aims that were enrolling subjects and have closed enrollment. Clinicaltrials.gov has been updated to reflect close of enrollment.

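### The only arm comparison written specifically for EEG ERD/ERS uses a direction-blind yes/no flag, and the plan does not settle whether a continuous comparison is also made

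*Combined protocol and SAP*

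**What the plan says.** The outcome lists in Background & Purpose and in Study Design both give the EEG map as secondary outcome 5 of Aim 1. It is a quantity on a continuous scale: "The EEG ERD/ERS, defined as the drop/rise in alpha (8-12 Hz) and beta (13-30 Hz) band power during attempted dorsiflexion" relative to idling. Study Design calls for a baseline for each outcome, then weekly, end-of-intervention and follow-up measurements.

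Statistical Considerations gives a shorter list: "the secondary outcomes are gait endurance, fall frequency, leg motor FM score, and dorsiflexion AROM and torque". EEG is not on it. The section then says that the LMM will be used for group differences in secondary outcomes, and later that the method for secondary outcomes resembles that for the primary.

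ERD/ERS gets a route of its own. A Mann-Whitney test compares each subject's assessments with that subject's baseline, looking for any significant change. From this, "each subject will be categorized as demonstrating significant changes in ERD/ERS or not". The flag is first related to gait improvement within each arm. The arms are then compared: "to determine if the presence of significant ERD/ERS changes was affected by group, the Chi-square test will be repeated", with the BCI-FES counts as observed and the control counts as expected values.

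**The concern.** The flag drops two things that the data contain. It drops the size of the change, so a change just past the threshold counts the same as a very large one. It also drops the direction, so a significant fall counts the same as a significant rise. The preliminary data were directional: ERD/ERS magnitude at Cz increased in 5 of the 6 subjects whose gait velocity improved. The flag also depends on how noisy each subject's recording is, because a noisy recording is more likely to be labelled as no change.

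Aim 1's hypothesis attributes the expected benefit to neural repair, and the flag comparison is the one EEG arm test written out for it. If it is the EEG result that counts, a real arm difference could be reported as no effect of group although the data could show it. If the LMM also covers EEG, there are two EEG group results that may disagree, with no rule for which one is reported.

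**Working it through.** **Inputs.** The power analysis is stated "with a significance level of 0.05"; sidedness is not given. Planned size: "A total of 80 subjects (which includes 10% attrition) will be randomized with 1:1 ratio into the two study arms", so 40 per arm. The progress report says "62 were randomized to study" in Aim 1, about 31 per arm if balanced. No ERD/ERS standard deviation, effect size, flag rate or power is given, so everything on EEG below is an assumption shown over a range.

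**The plan's own figure.** The only power figures for Aim 1 concern gait velocity: the "power analysis was based on a LMM with two treatment groups and 5 repeated measures (baseline and after weeks 1-4"). With variance 0.16, correlation 0.95 and times 0–4, the SD of a subject's slope is √(0.16 × 0.05 / 10) = 0.0283. A 35% advantage over 0.25 m/s in 4 weeks is a slope difference of 0.25 × 0.35 / 4 = 0.0219. Then z = 0.0219 / (0.0283 × √(2/40)) = 3.46, and power = Φ(3.46 − 1.96) = 93.3%, against 93.5% in Table 1. This supports a two-sided 5% test with 40 per arm. It says nothing about EEG.

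**Set-up for EEG.** Measure each subject's observed change in SD units: control N(m, 1), BCI-FES N(m + d, 1). Choose d so that a two-sided two-sample t-test has 80% power: d = 0.634 at 40 per arm, 0.723 at 31. Flag a subject when |change| > c, with c = 1.96/√(1 + k²). Here k is the between-subject SD of true change divided by the within-subject standard error, and k = 0, 1, 2, 3 gives c = 1.96, 1.386, 0.877, 0.620. The flag rate at mean μ is 1 − Φ(c − μ) + Φ(−c − μ). Compare the arms by an ordinary two-sample Pearson chi-square at 5%.

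**One case in full** (40 per arm, m = 0, k = 1). Control flag rate: 2 × (1 − Φ(1.386)) = 16.6%. BCI-FES: 1 − Φ(0.752) + Φ(−2.020) = 24.8%. Pooled rate 20.7%; standard error √(2 × 0.207 × 0.793 / 40) = 0.0906; z = 0.082 / 0.0906 = 0.905. Power ≈ Φ(0.905 − 1.96) + Φ(−0.905 − 1.96) = 14.8%. Exact enumeration gives the same.

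**Range over k = 0 to 3, exact enumeration (t-test 80% throughout):**

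| Mean change in controls | Flag power, 40 per arm | Flag power, 31 per arm |
|---|---|---|
| 0 | 11–15% | 12–17% |
| 0.25 SD | 21–31% | 22–33% |
| 0.5 SD | 30–44% | 31–47% |
| 1 SD | 40–61% | 39–61% |
| −d/2 (arms move equally in opposite directions) | about 5% | about 5% |

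In the last row the two flag rates are identical, so the test rejects only at its nominal level. Over control changes of 0–2 SD, flag power peaks near 63%.

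**Two further sensitivities.**
- The plan gives no rule for combining channels, bands and assessments into one flag. If many subjects are flagged (60–90% of controls, zero mean change, 40 per arm), power is about 5–9%.
- If the effect is not a uniform shift, the loss can be small. With 30% of BCI-FES subjects responding strongly and zero control change, one case gave 59% for the flag against 64% for the t-test.

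**The test as written.** Treating control counts as known expected values ignores half of the variance of the difference. The false-positive rate is therefore near 2 × (1 − Φ(1.96/√2)) = 16.6%; enumeration at 40 per arm gives about 16–24%. With zero control change this test rejects about 24–45% of the time at 40 per arm. That is not usable power, and the table does not describe it.

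**The case against.** The strongest reply is that a continuous arm comparison may already be planned. EEG is named as a secondary outcome in two places, and two sentences in Statistical Considerations apply the LMM, or a method like the primary one, to secondary outcomes. On that reading the flag is an addition and no power is lost. This stands as a possible reading. The same section nevertheless lists its secondary outcomes without EEG and then gives ERD/ERS a different method, so the text does not establish it. Nor does the text establish the opposite: a reader might infer that no continuous comparison will be made, and the documents do not support that either.

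A second reply is that a responder proportion is a fair descriptive target. It follows the preliminary study's presentation, and Aim 3 is the stated mechanism aim. That supports keeping the proportion as description. It does not support a flag without direction as the arm comparison.

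A third reply is that a figure of 11–17% depends on controls having no mean change. The control arm receives twelve two-hour sessions of active therapy and is assumed to gain 0.25 m/s in gait velocity, so some EEG change in that arm is plausible. This is right, and it is why the range is shown.

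**Conclusion.** The point holds as an unresolved and probably inefficient analysis of one secondary outcome. The only ERD/ERS-specific arm comparison discards size and direction, and the plan does not say whether the LMM covers EEG or which result counts. Severity is low to moderate.

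The illustrated loss, from 80% to about 11–17%, 21–33% or 40–61% according to the control mean change (0, 0.25 or 1 SD), assumes a uniform normal shift with equal SDs and a valid two-sample chi-square.

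Three stronger readings are tempting and are not supported:
- that an arm difference would be detected with under 20% power as a matter of fact. This needs zero control change, and the documents give no EEG figures to check it;
- that these figures describe the chi-square as written. They do not; its use of control counts as expected values is a separate defect, with an inflated false-positive rate;
- that some minimum loss is guaranteed. The responder case shows that the loss can nearly vanish.

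The case of arms moving equally in opposite directions shows what the flag cannot see. Nothing in the documents suggests that it is likely.

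**What to change.** In Statistical Considerations, Aim 1:

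- Add EEG ERD/ERS magnitude, alpha and beta separately, to the secondary outcomes analysed by the LMM, and state the channel set used.
- Name the EEG group result: the baseline-adjusted arm difference in signed change immediately after the intervention, with its confidence interval.
- Keep the proportion of subjects with individually significant change, reported separately for increases and decreases, as description without an arm test.

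The cost is wording only. The model is already in the plan, and the measurements are already scheduled in both arms. The progress report says that final assessments and data analysis are still to come, so the change can be dated and recorded before the EEG results are compared by arm. The small downside is that a mean difference in band power is less simple to state than a percentage of subjects; the descriptive proportions cover that.

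### Aim 1 tests the link between ERD/ERS change and gait gain by splitting both measures and running a separate chi-square in each arm, which has low power under the plan's own assumptions and does not compare the association between arms.

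*Combined protocol and SAP*

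**What the plan says.** In Statistical Considerations, Aim 1, ERD/ERS magnitude is compared with baseline by Mann-Whitney test and each subject is classed as having a significant change or not. Then "all subjects will also be categorized on whether they experienced a detectable increase in gait velocity", meaning a gain above 0.16 m/s from baseline. The two yes/no variables are set against each other within the BCI-FES arm: "A Chi-square test will be used to assess if there is a difference between the proportion of those with changes in ERD/ERS magnitude" among those whose gait improved. For the other arm, "This will also be repeated for the control group".

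A third chi-square compares how often significant ERD/ERS change occurs in the two groups, with the control group supplying the expected values.

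The section gives no expected counts, no power and no exact test for any of these. The Power Analysis covers only the mixed model (Aims 1 and 2) and the Aim 3 regression. For Aim 3, the same section plans a regression of gait velocity on group, the EEG-EMG measure w and their interaction, adjusted for baseline gait velocity.

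**The concern.** The 0.16 m/s cut lies below the mean gain that the plan assumes for both arms. If those assumptions are right, nearly everyone in the BCI-FES arm is improved, and the comparison rests on a handful of subjects. Splitting two measured quantities discards most of their information, and the chi-square approximation is doubtful when expected counts are small.

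Two separate within-arm tests also leave unanswered the question of whether ERD/ERS change relates to gait gain differently under BCI-FES than under conventional therapy. At stake is Aim 1's only planned analysis of change in brain signal against change in gait. A null result could reflect the method rather than the biology.

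**Working it through.** **Inputs from the documents**
- Control gain: "we assume conventional therapy will have an improvement of 0.25 m/s after 4 weeks of treatment". BCI-FES is taken as 30%, 35% or 40% better, that is 0.325, 0.3375 or 0.35 m/s.
- Spread: "the between-subject variance in gait velocity of about 0.16 m/s and the within-subject correlation of about 0.95". The figure 0.16 is used as a variance.
- Design: "5 repeated measures (baseline and after weeks 1-4) with a significance level of 0.05".
- Arm size: "A total of 80 subjects (which includes 10% attrition) will be randomized with 1:1 ratio into the two study arms", so 40 per arm, or 36 after 10% attrition. The Progress Report gives 62 randomised in Aim 1, about 31 per arm if split equally; arm counts are not given.
- Pilot (preliminary data): 6 of 9 improved at 1 month; ERD/ERS increased in 5 of those 6 and in none of the other 3.

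**Step 1: reproduce the plan's power.** For five equally spaced times and equal correlation, SE of the slope difference = sqrt(2 × variance × (1 − ρ) / (10n)).
- 35% effect, n = 40: difference per week = 0.25 × 0.35 / 4 = 0.0219; SE = sqrt(2 × 0.16 × 0.05 / 400) = 0.00632; power = Φ(3.46 − 1.96) = 93.3%. Table 1 states 93.5%.
- n = 30: 85.0%. The plan states 85%.
- All nine Table 1 cells agree within 2 points, so this is the plan's own model (two-sided 0.05).

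**Step 2: expected non-responders.** SD of change = sqrt(2 × 0.16 × 0.05) = 0.126 m/s. With normal change scores at week 4, P(gain > 0.16) = Φ((mean gain − 0.16) / 0.126).

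| Scenario | Improved | Not improved, of 40 / 36 / 31 |
|---|---|---|
| Control, 0.25 | 76.2% | 9.5 / 8.6 / 7.4 |
| BCI-FES +30% | 90.4% | 3.8 / 3.5 / 3.0 |
| BCI-FES +35% | 92.0% | 3.2 / 2.9 / 2.5 |
| BCI-FES +40% | 93.4% | 2.7 / 2.4 / 2.1 |
| Pilot rate, 3/9 not improved | 66.7% | 13.3 / 12.0 / 10.3 |

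**Step 3: expected counts.** With m non-responders, of whom a fraction q is expected to show ERD/ERS change, the two expected counts are mq and m(1 − q). The smaller is at most m/2, so it is below 5 whenever m is under 10. With m of 2 to 4, both are below 5.

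**Step 4: power and size by simulation.** Bivariate normal pairs, at least 6,000 arms per setting, uncorrected Pearson chi-square against a correlation test. Assumptions not in the documents: true correlation 0.5, and 50% to 60% of subjects with ERD/ERS change.
- BCI-FES at the 35% effect, 31 to 40 per arm: chi-square power about 12% to 28%, true size about 3%. A 30% effect leaves slightly more non-responders and raises power somewhat; a 40% effect lowers it.
- At the pilot response rate: about 44% to 55%.
- Continuous within-arm test: about 83% to 93%.
- At 31 per arm, an expected count is below 5 in all BCI-FES tables, and about 8% of those tables contain no non-responder.

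**Step 5: exact power, 36 subjects with 3 non-responders** (uncorrected / Yates / Fisher).
- ERD/ERS change in 70% against 30%: 33% / 11% / 21%.
- Pilot-sized contrast, 83% against 0%: about 100% / 91% / 98%.

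**Step 6: what the interaction can show.** By Fisher's z at 31 per arm, SE = sqrt(2/28) = 0.267. Correlations of 0.5 and 0: (0.549 − 0) / 0.267 = 2.06, power Φ(2.06 − 1.96), about 54%. Correlations of 0.5 and 0.2: 0.347 / 0.267 = 1.30, power Φ(1.30 − 1.96), about 25%.

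**The case against.** The count of 2 to 4 is not in the documents and depends on the hypothesised 30% to 40% advantage being real. If BCI-FES only matched control, 8.6 to 9.5 of 36 to 40 would not improve. At the pilot rate, the only observed response rate in the documents, it would be about 10 to 13. That rate is only a rough guide, because the pilot's significant improvement was not defined by 0.16 m/s and was taken at 1 month. These points make the count conditional. They do not remove the loss of power, which persists at the pilot rate.

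A reader might infer that the planned test would miss any real association. The documents do not support that: the pilot contrast of 5/6 against 0/3 would be detected even with 3 non-responders. Still, it comes from a post-hoc look at nine subjects, and a contrast such as 70% against 30% would usually be missed.

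A reader might also infer that the plan presents its two within-arm tests as a comparison of arms. It does not say so. The gap is only that no test of a difference in association is planned; the third chi-square concerns the frequency of ERD/ERS change alone. Aim 2 does not fill the gap, since its EEG modifiers are baseline features.

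Finally, the power of 83% to 93% belongs to a single-arm association. It must not be read as power for the proposed interaction, which Step 6 shows to be much lower.

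**Conclusion.** The point stands in conditional form. Under the plan's power assumptions, about 2 to 4 BCI-FES subjects would be non-responders at 31 to 40 per arm. The within-arm chi-square would then be conservative and, for a moderate association, weak: about 12% to 28% power at the 35% effect against about 83% to 93% for a continuous analysis. At the pilot response rate the gap narrows to about 44% to 55% against 83% to 93%. Only a contrast close to the pilot's would be found reliably. No planned test addresses whether the association differs by arm.

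This rests on normal change scores, equal correlation over time (supported by the match to Table 1), responder status judged at week 4 (the section does not name the assessment), an equal split of the 62 randomised for the figure of 31, and the assumed correlation and ERD/ERS frequency. The analysis is secondary and mechanistic. Nothing here bears on the primary mixed-model comparison of gait velocity.

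**What to change.** Replace the two within-arm chi-squares by one linear regression of week-4 gait velocity on baseline gait velocity, arm, continuous change in ERD/ERS magnitude, and arm by ERD/ERS change. This is the form the plan already uses for Aim 3.

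Define the ERD/ERS variable. The outcome definitions average magnitude across channels, while Statistical Considerations works channel by channel. Use the channel-averaged magnitude, with one model for each of the two frequency bands.

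Report the slope in each arm and the interaction, with 95% confidence intervals. State that the power gain applies to the slopes and that the interaction estimate will be imprecise. Keep the 0.16 m/s responder table as description, with Fisher's exact test if a p-value is wanted.

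The cost is revised analysis wording, a little more analysis work and a linearity assumption that should be checked by plot. No new data are needed. The Progress Report places data analysis in the next approval period, so the change can be made and dated before the final analysis.
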